8.1.3 Life-threatening

An adverse event or suspected adverse reaction is considered "life-threatening" if, in the view of either the investigator or sponsor, its occurrence places the participant or subject at immediate risk of death. It does not include an adverse event or suspected adverse reaction that, had it occurred in a more severe form, might have caused death. (21CFR312.32)

8.1.4 Severity

The severity of each Adverse Event will be assessed utilizing the CTCAE version 5.0.

8.1.5 Relationship to Study Product

All AEs will have their relationship to study product assessed using the terms: related or not related.

- Related – There is a reasonable possibility that the study product caused the adverse event. Reasonable possibility means that there is evidence to suggest a causal relationship between the study product and the adverse event.
- Not Related – There is not a reasonable possibility that the administration of the study product caused the event.

8.1.6 Adverse Events of Special Interest (AESI)

- Potential Drug Induced Liver Injury (DILI), positive Hy's Law, defined as:
 - AT (ALT or AST) elevation > 3 times upper limit of normal (ULN), AND
 - Total bilirubin > 2 times ULN, without initial findings of cholestasis (elevated serum alkaline phosphatase), AND
 - No other immediately apparent possible causes of AT elevation and hyperbilirubinemia, including, but not limited to, viral hepatitis, pre-existing chronic or acute liver disease, or the administration of other drug(s) known to be hepatotoxic.

8.2 ASSESSMENT OF SAFETY EVENTS

AE information collected will include event description, date of onset, assessment of severity and relationship to study product and alternate etiology (if not related to study product), date of

resolution of the event, seriousness and outcome. The assessment of severity and relationship to the study product will be done only by those with the training and authority to make a diagnosis and listed on the Form FDA 1572 as the site principal investigator or sub-investigator. AEs occurring during the collection and reporting period will be documented appropriately regardless of relationship. AEs will be followed through resolution.

SAEs will be:

- Assessed for severity and relationship to study product and alternate etiology (if not related to study product) by a licensed study physician listed on the Form FDA 1572 as the site principal investigator or sub-investigator.
- Recorded on the appropriate SAE report form, the medical record and captured in the clinical database.
- Followed through resolution by a licensed study physician listed on the Form FDA 1572 as the site principal investigator or sub-investigator.

For timeframe of recording adverse events, please refer to section **6.1**. All serious adverse events recorded from the time of first investigational product administration must be reported to the sponsor with the exception of any listed in section **8.4**.

8.3 REPORTING OF SERIOUS ADVERSE EVENTS

Any AE that meets protocol-defined serious criteria or meets the definition of Adverse Event of Special Interest that require expedited reporting must be submitted immediately (within 24 hours of awareness) to OSRO Safety using the CCR SAE report form. Any exceptions to the expedited reporting requirements are found in section **8.4**.

All SAE reporting must include the elements described in section **8.2**.

SAE reports will be submitted to the Center for Cancer Research (CCR) at: [contact] and to the CCR PI and study coordinator. CCR SAE report form and instructions can be found at: <https://nih.sharepoint.com/:u/r/sites/NCI-CCR-OCD-Communications/SitePages/Forms-and-Instructions.aspx?csf=1&web=1&e=uWBXtI>.

Following the assessment of the SAE by OSRO, other supporting documentation of the event may be requested by the OSRO Safety and should be provided as soon as possible.

8.4 WAIVER OF EXPEDITED REPORTING TO CCR

As death/hospitalization due to disease progression are part of the study objectives in the phase 2 portion of the study (PFS, OS, ORR), and captured as an endpoint in this study, they will not be reported in expedited manner to the sponsor during the phase II portion of the study. However, if there is evidence suggesting a causal relationship between the study drug and the event, report the event in an expedited manner according to section **8.3**.

8.5 SAFETY REPORTING CRITERIA TO THE PHARMACEUTICAL COLLABORATOR

Note: The PI/study team designee will be required to handle all reporting noted below to the pharmaceutical collaborator.

- For Non-Serious AEs:

- Adverse Events that are routinely collected according to GCP shall be submitted to BMS every three (3) months by the last working day of the third month.
- The collection of non-serious AE information should begin following the subject's study drug administration. All non-serious adverse events (not only those deemed to be treatment-related) should be collected continuously during the treatment period and for a minimum of 100 days following the last dose of study treatment, except for Grade 1 AEs, which will be collected and recorded for first 30 days on study only.
- Non-serious AEs should be followed to resolution or stabilization or reported as SAEs if they become serious. Follow-up is also required for non-serious AEs that cause interruption or discontinuation of study drug and for those present at the end of study treatment as appropriate.
- For Serious Adverse Events (SAEs):
 - All SAEs that occur following the subject's study drug administration through (100) days of discontinuation of dosing must be reported to BMS Worldwide Safety, whether related or not related to study drug.
 - An SAE report should be completed for any event where doubt exists regarding its seriousness
 - If the investigator believes that an SAE is not related to study drug, but is potentially related to the conditions of the study (such as withdrawal of previous therapy or a complication of a study procedure), the relationship should be specified in the narrative section of the SAE Report Form.
 - An appropriate SAE form (e.g. ex-US = CIOMS form or USA = Medwatch form) should be used to report SAEs to BMS. Note: Please include the BMS Protocol number on the SAE form or on the cover sheet with the SAE form transmission.
 - For studies with long-term follow-up periods in which safety data are being reported, include the timing of SAE collection.
 - The Sponsor will reconcile the clinical database AE cases (case level only) transmitted to BMS Global Pharmacovigilance ([contact]).
 - The Investigator will request from BMS GPV&E, [contact] the SAE reconciliation report and include the BMS protocol number every 3 months and prior to data base lock or final data summary
 - GPV&E will send the investigator the report to verify and confirm all SAEs have been transmitted to BMS GPV&E.
 - The data elements listed on the GPV&E reconciliation report will be used for case identification purposes. If the Investigator determines a case was not transmitted to BMS GPV&E, the case should be sent immediately to BMS ([contact]).
 - In addition to the Sponsor Investigator's responsibility to report events to their local HA, suspected serious adverse reactions (whether expected or unexpected) shall be reported by BMS to the relevant competent health authorities in all concerned countries according to local regulations (either as expedited and/or in aggregate reports).

- In accordance with local regulations, BMS will notify sponsor investigators of all reported SAEs that are suspected (related to the investigational product) and unexpected (ie, not previously described in the IB). An event meeting these criteria is termed a Suspected, Unexpected Serious Adverse Reaction (SUSAR). Sponsor investigator notification of these events will be in the form of either a SUSAR Report or a Semi-Annual SUSAR Report.
- Other important findings which may be reported by BMS as an Expedited Safety Report (ESR) include: increased frequency of a clinically significant expected SAE, an SAE considered associated with study procedures that could modify the conduct of the study, lack of efficacy that poses significant hazard to study subjects, clinically significant safety finding from a nonclinical study, , or sponsor or BMS decision to end or temporarily halt a clinical study for safety reasons.
 - Upon receiving an ESR from BMS, the investigator must review and retain the ESR with the IB. Where required by local regulations or when there is a central IRB/IEC for the study, the sponsor will submit the ESR to the appropriate IRB/IEC. The investigator and IRB/IEC will determine if the informed consent requires revision. The investigator should also comply with the IRB/IEC procedures for reporting any other safety information.

SAEs, whether related or not related to study drug, and pregnancies must be reported to BMS within 24 hours \ 1 Business Day of becoming aware of the event. SAEs must be recorded on either CIOMS, MedWatch, or approved site SAE form.

- Pregnancies must be reported and submitted to BMS. BMS will perform due diligence follow-up using the BMS Pregnancy Form which the investigator must complete.
 - SAE Email Address: [contact]
 - SAE [contact]
- If only limited information is initially available, follow-up reports are required. (Note: Follow-up SAE reports should include the same investigator term(s) initially reported.)
- If an ongoing SAE changes in its intensity or relationship to study drug or if new information becomes available, a follow-up SAE report should be sent within 24 hours \ 1 Business Day to BMS using the same procedure used for transmitting the initial SAE report.

BMS Safety Reporting. Study Team shall report to BMS all Serious Adverse Events. Reports shall be provided in accordance with applicable federal laws. Study Team shall comply with BMS's reasonable follow-up requests.

- Case-level Reconciliation.
 - Study Team shall perform case-level reconciliation as instructed by BMS to confirm BMS's receipt of all reports from Study Team. Study Team shall initiate reconciliation activity by e-mailing [contact] to request a reconciliation report.
 - Such reconciliation shall be performed quarterly, unless otherwise agreed by BMS in writing.
- Study Team shall comply with all applicable federal laws, including those related to data privacy, when undertaking these safety reporting-related obligations.

- Study Team shall promptly report to BMS all Product Quality Complaints (as defined at <http://www.globalbmsmedinfo.com>) associated with a BMS product no later than one (1) business day or three (3) calendar days, whichever is earlier after becoming aware of the event. Study Team shall report the information to [contact].

8.6 REPORTING PREGNANCY

All required pregnancy reports/follow-up to OSRO will be submitted to: [contact] and to the CCR PI and study coordinator. Forms and instructions can be found here: <https://nih.sharepoint.com/:u/r/sites/NCI-CCR-OCD-Communications/SitePages/Forms-and-Instructions.aspx?csf=1&web=1&e=uWBXtI>

8.6.1 Maternal exposure

If a participant becomes pregnant during the course of the study, the study treatment should be discontinued immediately, and the pregnancy reported to the Sponsor no later than 24 hours of when the Investigator becomes aware of it. The Investigator should notify the Sponsor no later than 24 hours of when the outcome of the Pregnancy becomes known,

Pregnancy itself is not regarded as an SAE. However, congenital abnormalities or birth defects and spontaneous miscarriages that meet serious criteria (section 8.1.2) should be reported as SAEs.

The outcome of all pregnancies should be followed up and documented.

If, following initiation of the investigational product, it is subsequently discovered that a study participant is pregnant or may have been pregnant at the time of investigational product exposure, including during at least 5 half-lives after product administration, the investigational product will be permanently discontinued in an appropriate manner (eg, dose tapering if necessary for participant).

The investigator must immediately notify [contact] of this event and complete one of the following forms within 24 hours of awareness of the event via either the CIOMS, MedWatch or appropriate Pregnancy Surveillance Form in accordance with SAE reporting procedures.

Protocol-required procedures for study discontinuation and follow-up must be performed on the participant.

8.6.2 Paternal exposure

Male participants should refrain from fathering a child or donating sperm during the study and for 6 months after the last dose of BMS-986253 or DNMTi.

Pregnancy of the participant's partner is not considered to be an AE. However, the outcome of all pregnancies occurring from the date of the first dose until 6 months after the last dose should, if possible, be followed up and documented. Pregnant partners may be offered the opportunity to participate in an institutional pregnancy registry protocol (e.g., the NIH IRP pregnancy registry study) to provide data about the outcome of the pregnancy for safety reporting purposes.

8.7 REGULATORY REPORTING FOR STUDIES CONDUCTED UNDER CCR-SPONSORED IND

Following notification from the investigator, CCR, the IND sponsor, will report any suspected adverse reaction that is both serious and unexpected. CCR will report an AE as a suspected adverse reaction only if there is evidence to suggest a causal relationship between the study product and the adverse event. CCR will notify FDA and all participating investigators (i.e., all investigators to whom the sponsor is providing drug under its INDs or under any investigator's IND) in an IND safety report of potential serious risks from clinical trials or any other source, as soon as possible, in accordance to 21 CFR Part 312.32.

All serious events will be reported to the FDA at least annually in a summary format.

8.8 SPONSOR PROTOCOL DEVIATION REPORTING

A Protocol Deviation is defined as any non-compliance with the clinical trial Protocol, Manual of Operational Procedures (MOP) and other Sponsor approved study related documents, GCP, or protocol-specific procedural requirements on the part of the participant, the Investigator, or the study site staff inclusive of site personnel performing procedures or providing services in support of the clinical trial.

It is the responsibility of the study Staff to document any protocol deviation identified by the Staff or the site Monitor in the CCR Protocol Deviation Tracking System (PDTs) online application. The entries into the PDTs online application should be timely, complete, and maintained per CCR PDTs user requirements.

In addition, any deviation to the protocol should be documented in the participant's source records and reported to the reviewing IRB per their guidelines. OSRO required protocol deviation reporting is consistent with E6(R2) GCP: Integrated Addendum to ICH E6(R1): 4.5 Compliance with Protocol; 5.18.3 (a), and 5.20 Noncompliance; and ICH E3 16.2.2 Protocol deviations.

9 CLINICAL MONITORING

Clinical site monitoring is conducted to ensure:

- that the rights of the participants are protected;
- that the study is implemented per the approved protocol, Good Clinical Practice and standard operating procedures; and
- the quality and integrity of study data and data collection methods are maintained.

Monitoring for this study will be performed by NCI CCR Office of Sponsor and Regulatory Oversight (OSRO) Sponsor and Regulatory Oversight Support (SROS) Services contractor. Clinical site monitoring activities will be based on OSRO standards, FDA Guidance E6(R2) Good Clinical Practice: Integrated Addendum to ICH E6(R1) March 2018, and applicable regulatory requirements.

Details of clinical site monitoring will be documented in a Clinical Monitoring Plan (CMP) developed by OSRO. CMPs will be protocol-specific, risk-based and tailored to address human subject protections and integrity of the study data. OSRO will determine the intensity and frequency of monitoring based on several factors, including study type, phase, risk, complexity, expected enrollment rate, and any unique attributes of the study and the site. The Sponsor will conduct a periodic review of the CMP to confirm the plan's continued appropriateness. A change

to the protocol, significant or pervasive non-compliance with GCP, or the protocol may trigger CMP updates.

OSRO SROS Monitoring visits and related activities will be conducted throughout the life cycle of each protocol. The first activity is before the study starts to conduct a Site Assessment Visit (SAV) (as warranted), followed by a Site Initiation Visit (SIV), Interim Monitoring Visit(s) (IMVs), and a study Close-Out Visit (COV).

Some monitoring activities may be performed remotely, while others will occur at the study site(s). Monitoring visit reports will describe visit activities, observations, and associated action items or follow-up required for resolution of any issues, discrepancies, or deviations. Monitoring reports will be distributed to the study PI, NCI CCR QA, CCR Protocol Support Office, coordinating center (if applicable), and the Sponsor regulatory file.

The site Monitor will inform the study team of any deviations observed during monitoring visits. If unresolved, the Monitor will request that the site Staff enter the deviations in the CCR Protocol Deviation Tracking System (PDTs) for deviation reporting to the Sponsor and as applicable per institutional and IRB guidance.

10 STATISTICAL CONSIDERATIONS

10.1 OBJECTIVES AND ENDPOINTS

OBJECTIVES	ENDPOINTS	JUSTIFICATION FOR ENDPOINTS
Primary		
Phase I: To determine OBD for BMS-986253 and RP2D, separately by cohort.	
 -Incidence of AEs, SAEs -AEs meeting protocol defined DLT criteria -AEs leading to discontinuation, death, and laboratory abnormalities. - OBD (RP2D) assessed during the first 30 days of treatment: - OBD will be the safest and lowest dose level showing optimal biological activity, defined as maximal suppression of serum free IL-8 levels.* 
*Maximal suppression of serum free IL-8 levels will be monitored for a goal of achieving IL-8 levels below the lower limit of detection of the assay in real time as outlined in Section 5.1.3.2 [ultrasensitive immunoassay based on Quanterix
	
standard endpoint for phase I protocol, see Section 3.1.1
 
Due to this being a targeted therapy, will pursue OBD instead of MTD as primary endpoint.

OBJECTIVES	ENDPOINTS	JUSTIFICATION FOR ENDPOINTS
	Simoa technology (lower limit of quantification = 0.86 pg/mL) by Myriad-RBM]	
Phase II: To determine efficacy as measured by overall response rate, separately by cohort.	-ORR per each cohort -assessed from first cycle until time of disease relapse, disease progression, or death, whichever occurs first, assessed every 3-6 months until 8 years.	Efficacy evaluation, standard for phase II protocol
Secondary		
Phase 1: To describe pharmacokinetic properties of BMS-986253 in MDS participants by cohort.	AUC, half-life, and steady state concentration Assessed during the first 30 days of treatment	Pharmacokinetic studies to evaluate for adequate absorption of therapy and define half-life/AUC and other properties of the study drug
Phase II: To evaluate safety and secondary clinical outcomes of BMS-986253 in MDS participants by cohort.	-Safety, as measured by: Incidence of AEs, SAEs; and AEs leading to discontinuation, death, and laboratory abnormalities, assessed from first cycle until time of disease relapse, disease progression, or death, whichever occurs first, assessed every 3-6 months - Clinical outcomes including: overall improvement rate (OIR), cytogenetic response rate, time to best response (CR, PR, marrow CR, or HI), disease free survival (DFS; definition: time to relapse for participants who achieve CR), progression free survival (PFS; definition: disease progression or death from MDS), leukemia free survival (LFS; definition: progression to AML or death from any cause), and overall survival (OS; definition:	Confirm safety and evaluate efficacy through long-term clinical outcomes

OBJECTIVES	ENDPOINTS	JUSTIFICATION FOR ENDPOINTS
	death from any cause); assessed every 3-6 months	
Exploratory		
To evaluate changes in serum cytokine levels pre- and post-treatment with BMS-986253.	Each of these will be evaluated using descriptive methods and reported as exploratory results. If any statistical tests are performed in these analyses, the results will be presented without adjustment for multiple comparisons but reported in the context of the number of tests performed. See section 5 for collection timepoints.	Evaluate mechanistic and immunologic effects of the study drug
To evaluate the cell composition in the peripheral blood and bone marrow microenvironment before and after treatment with BMS-986253.		
To evaluate changes in the transcriptome and proteome in response to treatment with BMS-986253.		
To determine the degree of bone marrow myeloid-derived suppressor cell (MDSC) infiltration.		
To describe changes in genetic clonal diversity during treatment with BMS-986253 in combination with DNMTi.		
To assess cell-autonomous effects on the MDS clone by measuring biomarkers in the Akt pathway (i.e. pS743) in MDS blasts.		
To evaluate cell-autonomous and microenvironment dependent activity of BMS-986253 using ex vivo culture of participant-derived		

OBJECTIVES	ENDPOINTS	JUSTIFICATION FOR ENDPOINTS
hematopoietic stem and progenitor cells.		
To assess quality of life improvement by participant reported outcomes using the EORTC QLQC30 score.		

10.2 SAMPLE SIZE DETERMINATION

The trial will begin with a phase I dose escalation phase using a standard 3+3 design to determine OBD, separately for each cohort. With 3 dose levels per cohort (and dose level -1), and no more than 6 participants per dose level, up to 18 participants may be enrolled in phase I per cohort, total 36 maximum.

In phase I/II, there will be two cohorts:

1. “Higher-risk” MDS (HR-MDS) Cohort with R-IPSS ≥ 3.5 : Intermediate and high-risk participants receiving combination treatment
2. “Lower-risk” MDS (LR-MDS) Cohort with R-IPSS < 3.5 : Lower intermediate and low-risk participants receiving single agent anti-IL8 treatment.

Based on the literature, DNMTi previously untreated participants with intermediate and high-risk disease have clinical response rates of approximately 20-50%; thus, in view of heterogeneity of prior results a response rate of at least 40% in participants treated with combination therapy would be desirable. [75, 116] In participants with low-risk disease, response rates are likely to be lower, and expected to be less than 30% from monotherapy;[84, 91, 92] thus, also attaining a response rate of at least 30% with monotherapy would be considered desirable.

Participants enrolled during phase I who are treated at the OBD may be included in the first stage portion of the trial if they meet the same eligibility as the participants in the phase II portion.

The two phase II cohorts will each have their own sample size determination:

- In participants in the higher-risk HR-MDS cohort (with either intermediate or high-risk MDS), the trial will be conducted using a Simon optimal two-stage phase II trial design to rule out an unacceptably low response rate (CR+PR+mCR with HI) of 30% ($p_0=0.30$)

in favor of an improved response rate of 50% ($p_1=0.50$) in order to determine if the combination will be able to potentially improve upon heterogeneous 20-50% response rates in participants who have received other agents. [75, 116] With $\alpha=0.10$ (probability of accepting a poor treatment=0.10) and $\beta=0.20$ (probability of rejecting a good treatment=0.20), the first stage will enroll 15 evaluable participants, including the 6 participants from the phase I dose escalation that reached OBD, and if 0 to 5 of the 15 has a response, then no further participants will be accrued. If 6 or more of the first 15 participants has a response, then accrual would continue until a total of 32 evaluable participants have been treated in that cohort. As it may take up to several months to determine if a participant has experienced a response, a temporary pause in the accrual may be necessary to ensure that enrollment to the second stage is warranted. If there are only 6-12 participants with a response out of 32 participants, this would be an uninterestingly low response rate. If there were 13 or more of 32 (40.6%) who experienced a response, treatment in this cohort would be sufficiently interesting to warrant further study in later trials. Under the null hypothesis (30% response rate), the probability of early termination is 72.2%.

- In participants with low-risk MDS, the trial will be conducted using a Simon optimal two-stage phase II trial design to rule out an unacceptably low response rate (CR+PR+mCR with HI) of 20% ($p_0=0.20$) in favor of an improved response rate of 40% ($p_1=0.40$) in order to determine if monotherapy with BMS-986253 will be able to improve upon an expected response rate below 30% in participants who have received other agents. [76, 83, 84] With $\alpha=0.10$ (probability of accepting a poor treatment=0.10) and $\beta=0.20$ (probability of rejecting a good treatment=0.20), the first stage will enroll 12 evaluable participants, including the 6 participants from the phase I dose escalation, that reached MTD, and if 0 to 2 of the 12 has a response, then no further participants will be accrued. If 3 or more of the first 12 participants has a response, then accrual would continue until a total of 25 evaluable participants have been treated in that cohort. As it may take up to several months to determine if a participant has experienced a response, a temporary pause in the accrual may be necessary to ensure that enrollment to the second stage is warranted. If there are only 3-7 participants with a response out of 25 participants, this would be an uninterestingly low response rate. If there were 8 or more of 25 (32.0%) who experienced a response, treatment in the appropriate cohort would be sufficiently interesting to warrant further study in later trials. Under the null hypothesis (20% response rate), the probability of early termination is 55.8%.

Secondary endpoints include progression free survival, overall survival, median survival, duration of response, and leukemia free survival. These will be determined separately in each of the phase II cohorts. Overall survival is considered an important endpoint in these participants and will be considered the most important secondary endpoint.

It is expected that up to 12-15 participants with MDS may be accrued per year. Thus, in order to accrue up to $18+18+32+25 = 93$ participants, it is expected that 4-5 years may be required to accrue the total number of required evaluable participants. In order to allow for a small number of inevaluable participants and potentially large number of screen failures, the accrual ceiling will be set at 200 participants.

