2 ELIGIBILITY ASSESSMENT AND ENROLLMENT

2.1 ELIGIBILITY CRITERIA

2.1.1 Inclusion Criteria

1. Participants must have histologically or cytologically confirmed MDS according to 2016 WHO criteria[1]
 - a. And:
2. have HR-MDS (R-IPSS ≥ 3.5) and received a minimum of 2 and maximum of 8 prior cycles for phase I and 4 for phase II of DNMTi therapy, or
3. have LR-MDS (R-IPSS <3.5),
 - a. and, at least one cytopenia:
 - i. granulocytes $< 1.0 \times 10^9/L$ and/or
 - ii. hemoglobin $< 110 \text{ g/L}$ with signs/symptoms of symptomatic anemia or transfusion-dependency
 - iii. platelets $< 100 \times 10^9/L$

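### Section 10.2 makes pooling of phase I participants into stage 1 optional and tied to phase II eligibility, then counts six of them outright; who belongs in the go/no-go count, and when that is settled, needs one rule

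*Combined protocol and SAP*

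**What the plan says.** Section 10.2 first gives a general statement about phase I participants treated at the OBD: they "may be included in the first stage portion of the trial if they meet the same eligibility as the participants in the phase II portion". It then sets out the two Simon designs. For HR-MDS, "the first stage will enroll 15 evaluable participants, including the 6 participants from the phase I dose escalation that reached OBD". For LR-MDS, "the first stage will enroll 12 evaluable participants, including the 6 participants from the phase I dose escalation, that reached MTD". Neither sentence repeats the eligibility condition, and the LR sentence refers to the MTD where the general statement and the HR sentence refer to the OBD.

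Section 2.1.1 sets different limits on prior treatment for HR-MDS: "received a minimum of 2 and maximum of 8 prior cycles for phase I and 4 for phase II of DNMTi therapy". For LR-MDS the Précis gives the same criterion for both phases.

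Phase I participants without a clinical response may be treated up to the C7D1 assessment (Section 3.1). The principal investigator reviews response data on each participant (Section 7.4.1), and no blinding is described. Section 10.4.6 requires a statistician's memo on the number of stage-1 responses, but does not say which phase I participants are in that number.

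**The concern.** The stage-1 count decides whether a cohort continues, so its membership should follow from the text alone. Here it does not. In HR-MDS a participant with 5 to 8 prior cycles who was treated at the OBD is excluded by the general statement and included by the cohort design. In LR-MDS eligibility does not differ between the phases; only the word *may* and the MTD/OBD wording are open.

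Two different consequences are possible, and they belong to different readings. If *may* leaves a choice, and the choice is made once the six responses are known, the false-positive rate can exceed the stated 0.10 ("probability of accepting a poor treatment=0.10"). If instead the six are always counted, ineligible HR participants can enter, and power suffers if they respond less often than the phase II population.

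**Working it through.** **Inputs (Section 10.2).** HR: p0 = 0.30, p1 = 0.50, stop if 5 or fewer of 15 respond, positive if 13 or more of 32. LR: p0 = 0.20, p1 = 0.40, stop if 2 or fewer of 12 respond, positive if 8 or more of 25. Nominal alpha is 0.10 and power 0.80 in both.

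**Step 1: reproduce the plan.** Write b(x; n, p) for the binomial probability, r1 and r for the largest non-promising counts, and n1 and n for the stage-1 and total sizes.

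- P(stop early) = Σ b(x; n1, p) for x = 0 to r1
- P(positive) = Σ b(x; n1, p) · P[Bin(n − n1, p) ≥ r + 1 − x] for x = r1 + 1 to n1

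| Cohort | Early stop under p0 | Alpha | Power |
|---|---|---|---|
| HR (5/15, 12/32) | 0.7216 | 0.0997 | 0.8038 |
| LR (2/12, 7/25) | 0.5583 | 0.0991 | 0.8151 |

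The early-stopping values match the stated 72.2% and 55.8%. These figures hold when inclusion does not depend on outcome and everyone counted responds at the same rate.

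**Step 2: all-or-none choice after responses are known.** Let K ~ Bin(6, p0) be the responses among the six. If K ≥ t, all six are counted and n1 − 6 new participants complete stage 1. Otherwise none is counted and stage 1 is entirely new. Let C(k) be the chance of a positive result given k responders among six counted:

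- C(k) = Σ b(y; n1 − 6, p0) · P[Bin(n − n1, p0) ≥ r + 1 − k − y], over y with k + y > r1
- Type I error = Σ b(k; 6, p0) · C(k) for k ≥ t, plus P(K < t) · alpha

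HR, t = 3: 0.1852 × 0.1948 + 0.0595 × 0.3547 + 0.0102 × 0.5353 + 0.0007 × 0.7035 + 0.7443 × 0.0997 ≈ 0.137.

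LR, t = 2: 0.2458 × 0.1552 + 0.0819 × 0.3267 + 0.0154 × 0.5449 + 0.0015 × 0.7631 + 0.0001 × 0.9171 + 0.6554 × 0.0991 ≈ 0.139.

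| Count the six if at least t respond | 0 | 1 | 2 | 3 | 4 | 5 | 6 |
|---|---|---|---|---|---|---|---|
| HR type I error | 0.0997 | 0.1107 | 0.1325 | 0.1374 | 0.1198 | 0.1046 | 0.1002 |
| LR type I error | 0.0991 | 0.1217 | 0.1394 | 0.1256 | 0.1070 | 0.1002 | 0.0991 |

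The maxima fall where C(k) first exceeds alpha: in HR, C(2) = 0.0845 and C(3) = 0.1948; in LR, C(1) = 0.0540 and C(2) = 0.1552.

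**Step 3: ineligible HR participants counted.** With m ineligible participants responding at rate q, the stage-1 count is Bin(m, q) + Bin(15 − m, p); the rest of the calculation is as in step 1. The documents give no response rate after 5 to 8 prior cycles, so q = 0.10 to 0.30 is an assumption.

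| m | Power, others at 0.50 (q = 0.10 to 0.30) | Type I error, others at 0.30 (q = 0.10 to 0.30) |
|---|---|---|
| 1 | 0.7505 to 0.7771 | 0.0828 to 0.0997 |
| 2 | 0.6874 to 0.7480 | 0.0676 to 0.0997 |
| 3 | 0.6146 to 0.7165 | 0.0543 to 0.0997 |
| 6 | 0.3563 to 0.6084 | 0.0249 to 0.0997 |

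On this reading type I error falls when q is below 0.30 and is unchanged at q = 0.30.

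**The case against.** The best defence is that the general statement already supplies the criterion. It stands in the same section, just before the cohort designs, and can be read as governing the six. Phase II eligibility can be settled from baseline data, so *may* can be read as permission conditional on eligibility, not as a free choice. The accrual sum of 18 + 18 + 32 + 25 = 93 subtracts no pooled participants, which fits conditional pooling. The prior-cycle limits overlap at 2 to 4 cycles, so the HR conflict may never arise. A positive result only supports further trials, and the response rate is reported with a 95% confidence interval.

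Most of this stands and limits the size of the point. It does not settle the text: the HR sentence counts a fixed six, phase I can supply people who fail the condition, and no section says when membership is fixed or that it is fixed without sight of responses.

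A reader might infer that the plan's type I error is about 14%. The documents do not support that, since nothing prescribes a choice made after responses are seen. A reader might go further and suppose that responders could be carried in one by one, which would give 23.5% (HR) and 22.0% (LR); no passage describes such selection. Nor can the alpha inflation and the power loss be added together, because one needs discretion and the other needs automatic inclusion.

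**Conclusion.** The inconsistency is real and sits in a decision rule. In HR-MDS it matters if any participant treated at the OBD had 5 to 8 prior cycles; in LR-MDS it is confined to the word *may* and to MTD versus OBD. The Simon boundaries themselves are sound.

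The type I error of 13.7% or 13.9% is the most that an all-or-none choice could produce. It requires that the choice be made after all six responses are known and at the most favourable cutoff. The power loss requires ineligible participants to be counted despite the stated condition, and depends on the assumed response rate. The six-of-six figure of 36–61% is the extreme; one or two ineligible participants give 75–78% or 69–75%. Neither is a prediction. Both are outcomes that the present wording fails to exclude and that a short clarification would.

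**What to change.** Use one rule throughout Section 10.2. Every phase I participant treated at the selected dose who met the phase II criteria at his or her own enrolment is included in stage 1; all others are excluded; and stage 1 is filled to 15 or 12 evaluable participants with new enrolments. Replace the fixed six in both cohort designs with the eligible participants, up to six. Reconcile MTD in the LR sentence with OBD elsewhere in the section. Record the included participants by study ID, from baseline eligibility data only, before any stage-1 responses are tabulated, and refer to that list in the interim memo of Section 10.4.6.

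The cost is a wording change, one short record and possibly a few more new stage-1 participants: at most six per cohort if none of the six qualifies. The planned 93 already allows for that, and the accrual ceiling is 200. The stated alpha and power are kept.
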